This study will be conducted as a randomized, placebo-controlled, double-blind trial, and both the participants and members of the research team directly involved with study participants and data analysis will be blinded to group assignment. Participants will be admitted to the inpatient CTRU on two occasions to complete baseline testing. Each of these visits will be scheduled ~5-10 days apart. Subjects will be asked to avoid caffeine and alcohol for at least 24 h, and to abstain from any structured intense exercise for 3 days before each admission. After participants complete baseline testing, they will be randomly assigned to treatment with either placebo or NMN, taken daily after breakfast for 16 weeks. *Placebo and NMN capsules will be provided at no charge by Shin-Kowa Pharma Company (Tokyo, Japan) (see letter from company president [name]).* During the treatment period, participants will be seen by the research coordinator and/or one of the study investigators every week. At each check in meeting, treatment compliance will be documented in a supplement accountability log based on the unused pill count and participant interview. These visits will also be used to address any study-related issues and help ensure body weight and physical activity remain constant during the study to avoid any potential confounding effects on the outcome measures. All testing conducted at baseline will be repeated after 16 weeks of treatment, and treatment will be continued until all repeat testing is completed. Metabolic testing performed during baseline visits 1 and 3 will be repeated in the same order after the 16-week treatment period.

Participants will be assigned a subject ID number upon entry to the study. The study ID is not related information about the individual and is not capable of being translated so as to identify the individual. Data and biological samples collected from study participants during the study participation will be labeled with the study ID and will *not* be used in combination with any personal identifiable information (PII). All data collected during the study will be de-identified and will not be used with any personal identifiable information.

C.3.1. Study outcomes. The effect of NMN therapy on the following outcomes will be assessed:

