Statistical evaluation of the study data will be carried out in collaboration with [name], who is an applied biostatistician with expertise in the design and analysis of clinical trials. Our primary analysis will be intention-to-treat in people with prediabetes. Preliminary analyses involving t-tests or Wilcoxon's test for continuous variables and chi square tests for dichotomous variables will be performed to confirm that baseline characteristics of subjects are similar in the placebo and NMN treatment groups. ANCOVA with the post-treatment value of the metabolic outcome measure (e.g., our primary outcome variable is insulin-mediated glucose uptake) as the dependent variable will be used to determine whether there are between group differences in the outcome measure after adjusting for the pre-intervention value and any measures that were significantly different before or during the intervention. We will explore the distributional properties of the metabolites; if the variables are skewed, we will analyze the data following a data transformation (e.g., a log transformation). If an appropriate transformation cannot be found, we will analyze the data semi-parametrically by using the ranks of the data. An exploratory goal of this study is motivated by preliminary data from rodents suggesting that the efficacy of NMN on the primary outcome may be greater in female than male animals. Therefore, we will evaluate the interaction between sex and treatment group by using analyses of covariance. These analyses should provide evidence regarding the possibility that efficacy differs according to the sex of the individual. We emphasize the exploratory nature of these analyses. This study is not powered to evaluate the relevant interaction term, and our purpose is to generate preliminary data to determine whether a subsequent larger study to assess the response to NMN based on sex is worthwhile.

Sample size considerations. The single primary endpoint in this study is insulin-mediated glucose Rd. All other endpoints are secondary. Because there is only one primary endpoint, the power computations for that endpoint are not adjusted for multiple testing. We also present power computations for important secondary endpoints below, but emphasize that the target sample size is based on considerations related to the primary outcome only.

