Using G*Power 3.1.9.2 and day-to-day variance we have previously reported in similar intervention studies [38, 60], we estimated that 22 participants/group will be needed to detect *realistic and physiologically and clinically meaningful* between-group differences in insulin-mediated glucose Rd [61, 62] with >90% power using a two-sided test and an α value of 0.05 in all primary outcomes listed below. Therefore, we will enroll 28 participants

in each group to ensure that an adequate number of participants complete the study (allowing for an estimated 6 drop-outs/group). All of the power computations below are based on a power of 0.9.

Insulin-mediated glucose Rd. We have reported day-to-day variability in insulin-mediated glucose Rd during high-dose insulin infusion (means \pm SD) to be 3.4 ± 6.1 $\mu\text{mol/kg FFM/min}$ in people with prediabetes. Using these SDs and assuming similar variance in the placebo and NMN groups, we estimate we will be able to detect a ~ 6.2 $\mu\text{mol/kg FFM/min}$ difference between groups in subjects with prediabetes ($\sim 14\%$ difference based on an expected mean glucose Rd at baseline of 44.5 $\mu\text{mol/kg FFM/min}$) [61].

Tissue gene expression. It is difficult to make robust estimates of our study power to detect changes in the molecular outcomes in adipose tissue and muscle, because of limited data evaluating these variables and the unknown effects of altering sleep. However, in our own experience, the day-to-day variance in muscle and adipose tissue gene expression is $\sim 30\%$ [52]. Accordingly, we estimate that we have $\geq 90\%$ power to detect statistically significant effect of NMN therapy in both people with prediabetes, if the differences from placebo are $>30.5\%$. Our previously published data [61] indicate that differences in adipose tissue gene expression of this magnitude are *realistic* in response to dietary and pharmacological intervention. Our study also has other (secondary) outcomes listed in Section C.3.1.b. These outcomes are important and we believe they will generate important information. However, it is difficult to estimate statistical power for these outcomes because of inadequate available information.

E. Retention and Recidivism plan.

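### The ANCOVA rule in Section D lets measures that diverge during treatment into the primary model, so the primary comparison can be conditioned on NMN's own effects

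*Combined protocol and SAP*

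**What the plan says.** Section D states the analysis principle as "Our primary analysis will be intention-to-treat in people with prediabetes" and the endpoint as "The single primary endpoint in this study is insulin-mediated glucose Rd". The model is "ANCOVA with the post-treatment value of the metabolic outcome measure (e.g., our primary outcome variable is insulin-mediated glucose uptake) as the dependent variable", and groups are compared after "adjusting for the pre-intervention value and any measures that were significantly different before or during the intervention". Because the primary outcome is the named example, the adjustment rule governs the primary analysis.

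Section D also plans baseline tests that "will be performed to confirm that baseline characteristics of subjects are similar in the placebo and NMN treatment groups". It does not list the measures eligible for adjustment, give the significance level for entry, limit entry to baseline variables, exclude other outcomes, or label the rule a sensitivity analysis.

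Three other places bear on the point:

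- Section B hypothesises that NMN improves all outcome measures relative to placebo.
- Section C.3 has weekly contacts that "help ensure body weight and physical activity remain constant during the study", so that changes in either do not confound the outcomes. This is the likely motive for the on-treatment part of the rule.
- Section C.3.3 stratifies randomisation by BMI (two strata) and sex, but Section D names neither as a covariate.

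**The concern.** Randomisation makes the arms comparable in what precedes treatment. It gives no such guarantee for what follows. If a measure differs between arms on treatment, either NMN changed it or the difference is chance. In the first case, adjusting for it removes from the estimate whatever part of the Rd difference is linked to that measure.

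The rule selects for this case: the more NMN changes a measure, the more likely that measure is to reach significance and enter the model. Two errors become possible. A real effect on Rd can be understated and missed. Where there is no effect on Rd, a spurious one can appear because NMN moved a measure that shares causes with Rd.

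A smaller weakness sits in the same sentence. Choosing baseline covariates by significance test ignores how prognostic they are and leaves the model open. It does not bias the randomised comparison in the way post-randomisation adjustment does.

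**Working it through.** **Inputs from Section D (Sample size considerations):** 22 evaluable per group, difference 6.2 and SD 6.1 µmol/kg FFM/min, two-sided alpha 0.05, power 0.9.

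**Assumptions, because the documents give no values:** NMN shifts one measure M by δ (in SDs of M), and M has within-arm correlation r with Rd. The range shown is δ 0.25 to 1.0 and r 0.3 to 0.5. Section D sets no significance level for entry, so p < 0.05 is assumed.

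**Step 1. Reproduce the plan's sample size.** n per group = 2 × (1.960 + 1.282)² × (6.1/6.2)² = 20.3, so 21 by the normal approximation. The noncentral t gives power 0.895 at 21 and 0.909 at 22. The stated 22 is reproduced, and 22 + 6 drop-outs = 28. The sample size is not in dispute.

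**Step 2. Change in the treatment coefficient once M is in the model.** Within arm, the slope of Rd on M is r × 6.1 per SD of M. The arms differ by δ SD in M, so the coefficient moves by −r × 6.1 × δ. For example, r 0.5 and δ 0.8 give −0.5 × 6.1 × 0.8 = −2.44, and 6.2 becomes 3.76.

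**Step 3. Chance that M enters.** This is the power of a two-sample t-test with noncentrality δ × √(22/2) = 3.317 δ.

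**Step 4. The whole rule, simulated.** 22 per arm, residual SD 6.1, M added only when its between-arm test has p < 0.05, several thousand trials per setting. Paired entries are for r 0.3 / r 0.5.

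| Shift δ | M enters | Change once in | Mean estimate (true 6.2) | Power | Type I error (true 0) |
|---|---|---|---|---|---|
| No such covariate | – | – | 6.2 | 0.90 | 0.05 |
| 0.25 SD | 13% | −0.46 / −0.76 | close to 6 | 0.89 to 0.90 | 0.05 |
| 0.5 SD | 37% | −0.92 / −1.53 | 5.7 / 5.3 | 0.84 / 0.82 | 0.06 / 0.08 |
| 0.8 SD | 74% | −1.46 / −2.44 | 5.0 / 4.1 | 0.72 / 0.61 | 0.10 / 0.21 |
| 1.0 SD | 90% | −1.83 / −3.05 | 4.4 / 3.3 | 0.57 / 0.41 | 0.14 / 0.35 |

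Repeat runs differ by about 0.02 in power and about 0.01 in type I error. The mean estimate is somewhat lower than entry probability times change would give. With positive r, M tends to enter in trials where chance has pushed both M and Rd up in the NMN arm, and to stay out where chance has pushed both down.

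**Step 5. Direction.** With positive r and no true effect, the mean estimate is negative: about −1.2 (r 0.3) and −2.2 (r 0.5) at 0.8 SD, so the false effect goes against NMN. With r −0.5 and 0.8 SD the mean is about +2.1 with rejection about 0.22, a false benefit.

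**Step 6. Chance entry only (δ = 0).** With k independent measures screened at 0.05, at least one enters with probability 1 − 0.95^k: 0.40 for k = 10 and 0.64 for k = 20. For 1 to 20 candidates the simulated mean estimate stays at about 6.2, power at 0.88 to 0.90 and type I error at about 0.04. There is no material bias.

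**The case against.** The best defence is that the on-treatment clause is meant for body weight and physical activity, the two variables that Section C.3 treats as confounders and asks staff to hold steady. If that succeeds, shifts should be small, and at 0.25 SD the rule does almost no harm. This stands as far as it goes, and it is why the lower end of the range belongs in the table. It does not rescue the wording. The clause covers any measure, both variables are still post-randomisation, and NMN could affect either.

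Stronger readings are tempting, and the documents do not support them:

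- **That every on-treatment difference biases the result.** Step 6 shows that chance differences do not. The 0.40 and 0.64 entry probabilities show only that the model is not fixed in advance. They also assume independent measures, whereas these outcomes are biologically related.
- **That a cause shared by the measure and Rd is enough to create a false effect.** NMN must also shift the measure.
- **That the rule contradicts intention-to-treat.** Every participant can still be analysed as randomised. What changes is the quantity estimated, which no longer fits the intention-to-treat aim.
- **That a false effect means a false benefit.** The sign follows r, and with positive r it goes against NMN.

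**Conclusion.** The point holds for the on-treatment part of the rule. As written, the plan allows the primary ANCOVA to adjust for consequences of NMN, and Section B expects such consequences. The estimate would then be an effect conditional on them, not the effect of assignment.

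The size runs from negligible at a 0.25 SD shift, through moderate at 0.5 SD, to serious at 0.8 to 1.0 SD, where power falls well below the planned 0.9 and type I error can reach 0.35. These figures rest on assumed shifts, correlations and entry level, and on a single affected measure. They show what the rule can do and do not predict what it will do in this trial.

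The case for changing the text rests on the principle and the trivial cost, not on any one row of the table. Significance-based choice of baseline covariates is a lesser weakness that the same edit removes.

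**What to change.** In Section D, remove the on-treatment part of the clause and the selection of covariates by significance, and state:

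> The primary model is post-treatment insulin-mediated glucose Rd on treatment, baseline Rd, BMI stratum and sex (the randomisation factors in Section C.3.3). No variable measured after randomisation enters the primary model.

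Name the factors explicitly, because the overview mentions separate randomisation by sex only, whereas Section C.3.3 gives both BMI and sex. Apply the same rule to the secondary-outcome ANCOVAs, each with its own baseline value. Report change in weight and physical activity by arm, and label any analysis that adjusts for them as exploratory.

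The cost is a sentence or two of text, settled before the data are unblinded. Sample size, visits and data collection do not change. In the simulation, the model without post-randomisation covariates keeps the mean estimate at 6.2 and power at 0.90 with 22 per group.
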